## **14. ASSESSMENT OF SAFETY**

### **14.1. Safety Parameters**

The safety and tolerability of ibrexafungerp will be monitored by clinical assessment of adverse experiences and by clinical and laboratory measurements, including vital signs (heart rate, blood pressure, and temperature), physical examinations, and laboratory safety tests [Table 5](#).

#### **14.1.1. Demographic/Medical History**

During screening, a complete medical history for the prior 1 year will be recorded for each participant. Medical history will include previous and current medical diagnoses, major surgical procedures as well as pregnancy, postpartum, and lactation history [Table 5](#).

#### **14.1.2. Vital Signs**

Vital signs, including blood pressure (BP systolic and diastolic), heart rate, respiratory rate, and body temperature will be measured at the time points indicated in the Schedule of Assessments in [Table 5](#).

Participants should be resting in a semi-recumbent position for at least 10 minutes prior to having vital sign measurements obtained. Semi-recumbent vital signs will include HR and BP.

The method for temperature collection will be oral or tympanic.

#### **14.1.3. Weight and Height**

Weight and height will be measured at the time points indicated in the Schedule of Assessments in [Table 5](#).

Body weight and height will be obtained with the participant's shoes off and jacket or coat removed.

#### **14.1.4. Physical Examination and Physical Activity Questioning**

A standard physical examination will be performed at the time points indicated in the Schedule of Assessments in [Table 5](#).

The examination will include assessment of skin, head, ears, eyes, nose, throat, neck, thyroid, lungs, heart, cardiovascular, abdomen, lymph nodes, and musculoskeletal system/extremities. Interim physical examinations will be performed at the discretion of the investigator, if necessary, to evaluate AEs or clinical laboratory abnormalities.

Participants will also be questioned as to any strenuous physical activity done prior to clinical admission. If strenuous physical activity was performed the investigator must notify the Sponsor prior to dosing the participant.

#### **14.1.5. Electrocardiogram (ECG)**

A 12-lead ECG will be obtained and evaluated by a physician for the presence of abnormalities at the time points indicated in the Schedule of Assessments in [Table 5](#).

Special care must be taken for proper lead placement. Participants should be resting in a semi-recumbent position for at least 10 minutes prior to having ECG readings obtained.

#### **14.1.6. Laboratory Assessments**

Blood and urine samples for laboratory assessments will be collected at the time points indicated in the Schedule of Assessments in [Table 5](#). Participants will not be required to fast prior to collecting blood and urine for laboratory safety tests. At screening a full set of laboratory tests (hematology, coagulation, chemistry and urinalysis) will be assessed; at pre-dose only hematology, AST, ALT, and bilirubin will be assessed; and at poststudy only hematology and clinical chemistry will be assessed (coagulation will not be required).

All laboratory hematology, coagulation, urinalysis, and chemistry values must be within normal limits or not clinically significant as determined by the investigator for the participant to be included in this study. Throughout the study clinical laboratory values will be reviewed by the investigator for significance and consideration as an AE. "Out of Range" values will be determined and reported by the laboratory performing the test as high or low with respect to the normal range for each laboratory value. Clinically significant laboratory test value abnormalities should be reported on the AE page of the eCRF as adverse events if they are determined to be clinically significant by the investigator.

##### **14.1.6.1. Hematology**

Hematology includes the following assessments:

White blood cell (WBC) count	Hemoglobin (HgB)
------------------------------	------------------

Red blood cell (RBC) count	Hematocrit (Hct)
Platelet count	

Differential white blood cell count will include percentages for segmented neutrophils, lymphocytes, monocytes, eosinophils, and basophils and absolute counts for neutrophils, lymphocytes, monocytes, eosinophils, and basophils.

#### 14.1.6.2. Coagulation

The coagulation profile includes the following assessments:

Prothrombin time (PT)
Activated partial thromboplastin time (aPTT)
Prothrombin time with international normalized ratio (INR)

#### 14.1.6.3. Blood Chemistry

Biochemistry testing includes the following assessments performed (fasting is not required for this study):

Alanine aminotransferase (ALT)	Magnesium
Albumin	Phosphorus
Alkaline phosphatase	Potassium
Aspartate aminotransferase (AST)	Sodium
Bicarbonate	Total bilirubin a
Calcium	Total creatine phosphokinase (CPK)
Chloride	Total Protein
Cholesterol	Triglycerides (TG)
Creatinine	Urea
	Gamma-glutamyl transferase (GGT)

a Bilirubin will be fractionated if total bilirubin is elevated. For all total bilirubin results above the upper limit of normal, obtain direct bilirubin value, including at screening and poststudy.

#### 14.1.6.4. Urinalysis

Urinalysis includes the following assessments:

Dipstick:	Microscopic:
Protein	WBC
Glucose	RBC
pH	Epithelial cells
	Casts (specify)

#### 14.1.6.5. Alcohol and Urine Drug Screens

Alcohol, and urine drug screens (site standard urine drug screen) will be collected at the time points indicated in the Schedule of Assessments in [Table 5](#).

#### **14.1.6.6. Virus Serology**

HIV/Hepatitis screens will be collected at the time points indicated in the Schedule of Assessments in [Table 5](#).

#### **14.1.6.7. Pregnancy Screen**

Pregnancy tests will be collected at the time points indicated in the Schedule of Assessments in [Table 5](#). The serum pregnancy testing will have a sensitivity of at least 25 mIU/L.

#### **14.1.6.8. COVID Screen**

COVID testing will be performed per the site's protocol at the time points indicated in the Schedule of Assessments in [Table 5](#).

#### **14.1.6.9. Adverse Event and Concomitant Medication Assessments**

Adverse events will be collected from the time of informed consent throughout the study, up through the poststudy visit.

All medications (both prescription and OTC) taken within 14 days before dosing with study medication throughout the study, and through poststudy visit will be recorded on the eCRF.

#### **14.1.7. Blood Volume Requirements**

Approximately 116.5 mL of blood will be collected from participants (see [Table 6](#)).

**Table 6: Blood Volume Table**

Laboratory Test	Number of Collections	Amount per Collection	Total Amount per Participant
Laboratory safety tests	3	15.5 mL	46.5 mL
Blood for ibrexafungerp concentration	10	4 mL	40 mL
Serum for $\beta$ -hCG test	3	10 mL	30 mL
TOTAL			116.5 a

a If additional pharmacokinetic and/or safety analysis is necessary, additional blood (up to 25 mL) may be obtained.

### **14.2. Adverse and Serious Adverse Events**

#### **14.2.1. Definition of Adverse Events**

An AE is any untoward medical occurrence associated with the use of a drug in humans, whether or not considered drug related. An AE can therefore be any unfavorable and unintended sign (including an abnormal laboratory finding), symptom, or disease temporally associated with the use of a study drug/study intervention, whether or not related to the study drug/study intervention.

Any laboratory abnormality that is deemed to be clinically significant in the opinion of the investigator will be considered an adverse event and should be recorded in the eCRF, whether or not it is related to study drug.

Stable chronic conditions that are present prior to clinical trial entry and do not worsen are not considered adverse events and will be accounted for in the participant's medical history.

The following can be considered AEs:

- An exacerbation of a pre-existing illness
- An increase in frequency or intensity of a pre-existing episodic event or condition
- A condition detected or diagnosed after the initiation of treatment with study medication, even though it may have been present prior to the start of the study
- Continuous persistent disease or symptoms present at baseline that worsen after informed consent or following the initiation of treatment with study medication

The following are **not** considered AEs:

- Medical or surgical procedures (e.g., surgery, endoscopy, tooth extraction, or transfusion); the condition that leads to the procedure is an AE
- Pre-existing disease or conditions present or detected at the start of the study that do not worsen
- Situations where an untoward medical occurrence has not occurred (eg, hospitalizations for cosmetic surgery or elective surgery or social/convenience admissions)

#### **14.2.1.1. Serious Adverse Event (SAE)**

A serious adverse event is an AE occurring during any study phase (ie, baseline, treatment, or follow-up), and at any dose of the investigational product, comparator or placebo, that fulfils one or more of the following:

- Results in death
- It is immediately life-threatening
- It requires in-patient hospitalization or prolongation of existing hospitalization
- It results in persistent or significant disability or incapacity or substantial disruption of the ability to conduct normal life functions
- Results in a congenital abnormality or birth defect
- It is an important medical event that may jeopardize the participant or may require medical intervention to prevent one of the outcomes listed above.

All SAEs that occur after any participant has been enrolled, before treatment, during treatment, through the post-study visit following the cessation of treatment, whether or not they are related to the study, must be recorded on forms provided by SCYNEXIS, Inc.

#### **14.2.1.2. Other Adverse Event (OAE)**

OAEs will be identified by the Drug Safety Physician and if applicable also by the Clinical Study Team Physician during the evaluation of safety data for the Clinical Study Report. Significant adverse events of particular clinical importance, other than SAEs and those AEs leading to discontinuation of the participant from the study, will be classified as OAEs. For each OAE, a narrative may be written and included in the Clinical Study Report.

#### **Events of Clinical Interest**

The following are considered events of clinical interest (ECIs), and must be reported within 24 hours of the site becoming aware of the ECI:

- Overdose
- ALT or AST  $>3 \times$  ULN, confirmed by repeat
- Hypersensitivity Reactions

### **Overdose**

An overdose occurs if a participant has taken, accidentally or intentionally, any drug administered as part of the protocol in a dose exceeding that prescribed by the protocol. An overdose (and any associated AE) is considered an ECI and must be reported within 24 hours of the site becoming aware of the overdose.

#### **14.2.2. Unexpected Adverse Event**

An AE is considered “unexpected” if it is not listed in the Brexafemme® Package Label, Investigator’s Brochure (IB), or is of greater specificity or severity than has been observed with the particular study drug being tested. For example, under this definition, hepatic necrosis would be unexpected (by virtue of greater severity) if the IB referred only to elevated hepatic enzymes or hepatitis. Similarly, cerebral thromboembolism and cerebral vasculitis would be unexpected (by virtue of greater specificity) if the investigator’s brochure listed only cerebral vascular accidents. “Unexpected,” as used in this definition, also refers to AEs that are mentioned in the IB as occurring with a class of drugs or as anticipated from the pharmacological properties of the drug but are not specifically mentioned as occurring with the particular drug under investigation.

#### **14.2.3. AE and SAE Follow-up**

All AEs and SAEs will be followed to resolution (the participant’s health has returned to his or her baseline status or all variables have returned to normal) or until an outcome is reached, stabilization occurs (the investigator does not expect any further improvement or worsening of the event), or the event is otherwise explained, regardless of whether the participant is still participating in the study. All appropriate therapeutic measures should be undertaken and recorded. Where appropriate, medical tests and examinations will be performed to document resolution of the event(s).

One of the following terms should be used to report the outcome of an event:

Recovered/Resolved: The event has fully recovered. If the event was a worsening of an underlying medical condition, the event is considered recovered when the condition has returned to the initial level.

Not recovered/Not resolved: The event was ongoing at the time of the report.

#### **14.2.4. Medical Emergencies**

All equipment, supplies, and the properly skilled medical personnel must be accessible for an adverse event requiring immediate treatment.

After a medical emergency has been safely managed, it needs to be reported as soon as possible, but within 24-hours to the safety physician, the SCYNEXIS, Inc. medical monitor and any

appropriate reporting done to the ethics committee and the appropriate regulatory agencies in the necessary time frames.

#### **14.2.5. Protocol Deviations for an Adverse Event**

In the event of an adverse event or medical emergency, allowing departures from the protocol will be decided on a case-by-case basis. The Investigator or other physician in attendance in such an emergency must contact the SCYNEXIS, Inc. medical monitor, as soon as possible after the medical emergency has been managed, to discuss the circumstances of the emergency. The Investigator, in consultation with the SCYNEXIS, Inc. medical monitor, will decide whether the participant should continue to participate in the study. The Investigator and the SCYNEXIS, Inc. medical monitor will document this decision. The Investigator will inform the ethics committee of all protocol deviations in accordance with the ethics committee established procedure. No deviations from the protocol of any type will be made without complying with all ethics committee -established procedures.

#### **14.2.6. Additional Needed Clinical Laboratory Tests**

Clinical laboratory tests other than those specified in the protocol may be performed to ensure the safety of the participants. Those circumstances and data (dates, times, tests and all notes and results) will be documented on an eCRF.

#### **14.2.7. Relationship to Study Drug**

An Investigator who is qualified in medicine must make the determination of relationship to the investigational product for each AE (Unrelated, Possibly Related or Probably Related). The Investigator should decide whether, in his or her medical judgment, there is a reasonable possibility that the event may have been caused by the investigational product. If no valid reason exists for suggesting a relationship, then the AE should be classified as “unrelated.” If there is any valid reason, even if undetermined, for suspecting a possible cause-and-effect relationship between the investigational product and the occurrence of the AE, then the AE should be considered “related”.

If the relationship between the AE/SAE and the investigational product is determined to be “possible” or “probable” the event will be considered to be related to the investigational product for the purposes of expedited regulatory reporting.

#### **14.2.8. Recording Adverse Events**

Adverse events spontaneously reported by the participant and/or in response to an open question from the study personnel or revealed by observation will be recorded during the study at the investigational site. Clinically significant changes in laboratory values, blood pressure, and pulse need not be reported as AEs. However, abnormal values that constitute an SAE or lead to discontinuation of administration of study drug must be reported and recorded as an AE. Information about AEs will be collected from the time informed consent is obtained up through the poststudy visit. Serious Adverse Event information will be collected from time informed consent is obtained through the poststudy visit. The AE term should be reported in standard medical terminology when possible. For each AE, the investigator will evaluate and report the

onset (date and time), resolution (date and time), intensity, causality, action taken, serious outcome (if applicable), and whether or not it caused the participant to discontinue the study.

Intensity will be assessed according to the following scale:

- Mild (awareness of sign or symptom, but easily tolerated)
- Moderate (discomfort sufficient to cause interference with normal activities)
- Severe (incapacitating, with inability to perform normal activities)

It is important to distinguish between serious and severe AEs. Severity is a measure of intensity whereas seriousness is defined by the criteria under Section 14.2.1.1. An AE of severe intensity may not be considered serious.

Should a pregnancy occur, it must be reported and recorded on SCYNEXIS, Inc.'s pregnancy form. Pregnancy in itself is not regarded as an AE unless there is a suspicion that an investigational product may have interfered with the effectiveness of a contraceptive medication.

The outcome of all pregnancies (spontaneous miscarriage, elective termination, normal birth or congenital abnormality) must be followed up and documented even if the participant was discontinued from the study.

All reports of congenital abnormalities/birth defects are SAEs. Spontaneous miscarriages should also be reported and handled as SAEs. Elective abortions without complications should not be handled as AEs.

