**Table 5: Schedule of Assessments (Continued)**

Study Procedures	Screening a	Day 1					Day 2	Day 3	Day 4	Day 5 Poststudy
		Predose b	0 hr	8 hr	12 hr	24 hr	36 hr	48 hr	72 hr	108 hr
Admission to Clinic and Discharge from Clinic k		X								X
Adverse Event Monitoring		X-----								X
Prior/Concomitant Medication		X-----								X

Abbreviations: BP = blood pressure; HR = heart rate; RR = respiratory rate, PK = pharmacokinetic, ECG = electrocardiogram, and HIV = human immunodeficiency virus

a Pre-study screening to determine eligibility may be performed within 4 weeks prior to dosing with study medication.

b The Day 1 predose examinations and assessments may be performed up to 12 hours predose.

c During physical examination at screening and predose participants will also be asked about physical activity. Prior to ECG the participants must be in a semi-recumbent position for at least 10 minutes prior to having heart rate, blood pressure, and ECG performed.

d Height documented at screening only.

e Participants will not be required to fast prior to collecting blood and urine for laboratory safety tests. At screening a full set of laboratory tests (hematology, coagulation, chemistry, and urinalysis) will be assessed; at pre-dose only hematology, AST, ALT, and bilirubin will be assessed; and at poststudy only hematology and clinical chemistry will be assessed (coagulation will not be required).

f Urine drug and alcohol screening will be done at screening, within 12 hours before the first dose, and upon admission to the clinic. COVID-19 testing will be done per site requirements.

g Ibrexafungerp 300-mg will be administered BID Q12H on Day 1 while the participant is in a semi-supine position with 240 mL of room temperature water.

h Plasma samples will be obtained at the following timepoints: 0 hours (prior to first dose), and at 2, 6, 8, 12, 24, 36, 48, 72 and 108 hours post first dose of study drug for determination of ibrexafungerp in plasma concentrations. The 12-hour samples will be taken prior to the second dose of ibrexafungerp.

i Breast Milk: **complete expression** of milk from both breasts (using a standard electric breast pump) will be obtained at the following timepoint and intervals: pre-dose, 0-2, 2-4, 4-8, 8-12, 12-18, 18-24, 24-36, 36-48, 48-72, and 72-108 hours post first dose of study drug.

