5.8.2 Clinical Laboratory Assessments

Hematology, coagulation, blood chemistry, urinalysis, alcohol, and urine drug screens, pregnancy screen, serology, and COVID-19 test will be performed as described in the schedule of assessment [Table 1](#).

Descriptive statistics for baseline value, actual value will be provided for clinical hematology, coagulation, chemistry laboratory tests and quantitative urinalysis including pH. The change from baseline value to Day 5 post study will be provided for hematology

and clinical chemistry. Baseline for clinical laboratory tests is defined as the last non-missing assessment prior to administration of study drug. Conventional Units will be used for reporting the laboratory test results. Unscheduled lab visit assessments will be excluded from summary tables but will be provided in the listings.

Values for any chemistry, hematology, coagulation and urinalysis values outside the clinical reference ranges, clinically significant or not will be flagged on the individual participant data listings. Laboratory test results will be assigned a low/normal/high (L/N/H) classification according to whether the value is below (low, L), within (normal, N), or above (high, H) the laboratory parameter's reference range. Shifts from baseline (L/N/H) to Day 5 post study (L/N/H) will be presented for hematology and clinical chemistry only.

Plots will be generated for laboratory parameters, including the absolute values and change from baseline values for hematology and clinical chemistry.

Alcohol and urine drug screens, serology, COVID-19 test, pregnancy screen results will be listed by participant.

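### The protocol gives opposite instructions on whether a clinically significant laboratory abnormality is an AE, and two different end dates, 26 days apart, for SAE collection.

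*Protocol*

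**What the plan says.** **Laboratory abnormalities.** Three protocol sections address the same trigger, an abnormality that is clinically significant.

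- 14.1.6 (Laboratory Assessments): "Clinically significant laboratory test value abnormalities should be reported on the AE page of the eCRF as adverse events", on the investigator's determination of significance.
- 14.2.1 (Definition of Adverse Events): "Any laboratory abnormality that is deemed to be clinically significant in the opinion of the investigator will be considered an adverse event". It is to be recorded in the eCRF whether or not it is related to study drug.
- 14.2.8 (Recording Adverse Events): "Clinically significant changes in laboratory values, blood pressure, and pulse need not be reported as AEs". The exceptions follow at once: "abnormal values that constitute an SAE or lead to discontinuation of administration of study drug must be reported and recorded as an AE".

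The Events of Clinical Interest subsection lists ALT or AST above 3 x ULN, confirmed by repeat. Such events "must be reported within 24 hours of the site becoming aware of the ECI".

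**SAE window.**

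- 14.2.8: "Serious Adverse Event information will be collected from time informed consent is obtained through the poststudy visit".
- 14.2.1.1 also stops at the post-study visit, but starts at enrolment rather than consent.
- 14.2.9 records all SAEs, related or not, from consent to 30 days after the last dose. It also keeps possibly or probably related SAEs reportable at any later time.
- Appendix B refers only to the course of the study.
- SAP 5.8.1 collects AEs to the post-study visit and gives no separate SAE window.

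**The concern.** Safety and tolerability is a stated secondary objective, and one or two sites will collect the data from very few women. With conflicting instructions, the same Day 5 result could be an AE with coding, causality and intensity at one site, and only a flagged laboratory value at another. Raised liver enzymes are a named potential risk in 9.4.1. Under 14.2.8, a confirmed ALT or AST above 3 x ULN could be an event of clinical interest with no matching TEAE entry.

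For SAEs, the section a site follows decides whether a new-onset unrelated event in the weeks after discharge is captured at all. The SAP's TEAE definition has no end date, so such an event would enter the serious-TEAE counts if it were recorded.

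**Working it through.** The plan states no figure on this point, so there is none to reproduce. The check compares the texts and does arithmetic on the schedule.

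**Inputs**

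- Doses at 0 h and 12 h on Day 1, none later (Protocol 11.7.3).
- Post-study visit on Day 5, at 108 h after the first dose (11.7.5, Table 5).
- Post-dose safety laboratory tests: "at poststudy only hematology and clinical chemistry will be assessed (coagulation will not be required" (Table 5, footnote e). No other post-dose draw is scheduled.
- 30-day SAE end, counted from the last dose (14.2.9).
- 5 participants at the interim analysis and up to 10 in all, assuming no replacements.

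**1. Can the exceptions in 14.2.8 remove the laboratory conflict?**

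Scheduled draw minus last dose: 108 - 12 = 96 h, or 4 days after dosing has ended. No scheduled post-dose result can lead to stopping study drug, so that exception covers 0 of the 1 x 5 = 5 to 1 x 10 = 10 scheduled draws. Only the SAE exception remains.

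| Day 5 result | 14.1.6 and 14.2.1 | 14.2.8 |
|---|---|---|
| Not clinically significant | not an AE | not an AE |
| Clinically significant, not serious | AE | need not be an AE |
| Constitutes an SAE | AE | AE |

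The conflict is confined to the middle row.

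**2. Step size.** One event recorded or not moves a TEAE term by 1/5 = 20 percentage points, or 1/10 = 10. This is a unit of change, not an expected effect.

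**3. SAE window, from the first dose**

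- Post-study end: 108 h = 4.5 days.
- 30-day end: 12 + 30 x 24 = 732 h = 30.5 days.
- Gap: 732 - 108 = 624 h = 26 days per woman.
- In all: 5 x 26 = 130 to 10 x 26 = 260 participant-days, with no assessment scheduled.

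The difference between collecting (14.2.8) and recording (14.2.9) does not reconcile the windows, because 14.2.1.1 also speaks of recording and stops at the post-study visit.

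**4. Does the stated duration settle the end date?** Protocol 9.1 gives about 4 to 5 weeks from pre-study through post-study monitoring. With the full 28-day screening window, a Day 5 end gives about 28 + 5 = 33 days (4.7 weeks). The 30-day end gives about 28 + 31 = 59 days (8.4 weeks). The duration fits Day 5 better, but that does not cancel the explicit instruction in 14.2.9.

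**5. Follow-on in the SAP.** Appendix A caps an imputed AE stop date at the data cutoff or the end of study, whichever is earlier. SAP 5.5 labels Day 5 the end of study. If Appendix A means the same day, an SAE that starts later and has a partial stop date would be given a stop date before its own onset.

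**The case against.** The strongest reply is that 14.2.8 is permissive. A site that records every clinically significant laboratory abnormality complies with all three sections, so the fault is a loose exemption rather than incompatible orders. That is true of a site that chooses to record. A site that uses the exemption omits events that 14.2.1 defines as AEs and 14.1.6 tells it to report, so the conflict stands.

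The consequence is also limited:

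- SAP 5.8.2 lists and flags abnormal values and adds shift tables: "Shifts from baseline (L/N/H) to Day 5 post study (L/N/H) will be presented for hematology and clinical chemistry only".
- Events of clinical interest are counted in the SAP's AE summary and listed. This does not create a system organ class and preferred term entry with causality and intensity.
- Related SAEs remain reportable at any time, and known events are followed to outcome (14.2.3). The gap is therefore mainly new-onset SAEs judged unrelated, 4 to 30 days after the last dose.
- No statistical testing of safety is planned, and PK, milk-to-plasma ratio and infant dose are unaffected.

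Four narrower points are fair:

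- The stop-date problem needs several conditions together, and no summary in SAP 5.8.1 uses AE duration.
- Replacements could take the number treated above 5 or 10, so the totals above are conditional.
- No section explicitly requires blood pressure or pulse changes to be AEs. That part of 14.2.8 is in tension only with the general AE definition.
- The different SAE start in 14.2.1.1 is minor, because that section does not exclude earlier events.

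**Conclusion.** Both inconsistencies are in the current protocol text and should be corrected. Neither the exceptions in 14.2.8 nor the SAP resolves them. The laboratory conflict covers non-serious, clinically significant results at the single scheduled post-dose draw. The SAE conflict covers 26 days per woman. How many events fall in either gap cannot be derived from the documents, which give no event rates. The conclusion rests on reading the post-study visit as Day 5 at 108 h, as 11.7.5 and Table 5 place it, and on scheduled assessments only. The effect is on the completeness and comparability of AE and SAE records. The documents lean towards a Day 5 SAE end but do not settle it.

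**What to change.** 1. Remove laboratory values from the exemption in 14.2.8, so that it agrees with 14.1.6 and 14.2.1. This is the smallest edit, because two sections already require recording.
2. State explicitly whether clinically significant blood pressure and pulse changes are AEs.
3. State one SAE start and one SAE end, in identical terms, in 14.2.1.1, 14.2.8, 14.2.9, Appendix B and SAP 5.8.1. The sponsor must say which end is intended.
4. If the end falls after Day 5, align the stop-date cap in SAP Appendix A and say what end of study means there.

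The cost is wording in the next amendment and in the SAP before database lock, and perhaps a few more AE entries. If the 30-day end is kept, the study also needs a way to learn of SAEs after discharge, since nothing is scheduled after 108 h.
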